### **7.1.3. Vital Signs**

Blood pressure, pulse rate, respiratory rate, and oral body temperature will be assessed with the subject sitting at rest for at least 5 minutes at the times indicated in the Schedule of Assessments in [Appendix 5](#). Vital signs may also be performed at other times if judged to be clinically appropriate or if the ongoing review of the data suggests a more detailed assessment of vital signs is required.

Day 1 predose blood pressure, pulse rate, and respiratory rate will be measured in triplicate at approximately 2-minute intervals. The median value will be used as the baseline value in the data analysis. All subsequent measurements will be performed singly and repeated once if outside the relevant clinical reference ranges. Oral body temperature will be measured singly.

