At study visits when study treatment is to be administered, the following schedule of spirometry assessments (forced expiratory maneuvers) is recommended:

- a minimum of 3, maximum of 6 maneuvers within 60 minutes predose
- preferably 3 but a minimum of 2 maneuvers as soon as feasible but within 15 minutes after completion of dose administration
- preferably 3 but a minimum of 2 maneuvers at  $30 \pm 5$  minutes after completion of dose administration
- preferably 3 but a minimum of 2 maneuvers at  $60 \pm 10$  minutes after completion of dose administration
- preferably 3 but a minimum of 2 maneuvers at  $90 \pm 15$  minutes after completion of dose administration

The maximum number of forced expiratory maneuvers in any day should not exceed 16. The minimum number of maneuvers at study visits when study treatment is to be administered should be 11 but it is acknowledged this may be too taxing for an individual with IPF. The Investigator should use clinical judgement to balance the safe monitoring of the subject for possible bronchoconstriction following study treatment against the burden of this testing. Greater emphasis should be placed on proper assessment closer to the time when treatment is completed than at later times. In the absence of evidence of bronchoconstriction and if the subject is not able to perform the schedule of assessments proposed above, the Investigator may alter the timing of postdose spirometry sessions, ie, spread them out over a longer interval, or may reduce the number of postdose spirometry sessions. The Investigator may not alter the specified predose spirometry assessment. At every postdose spirometry session, a minimum of 2 forced expiratory maneuvers must be attempted.

If the Investigator implements changes to the proposed postdose spirometry assessments, the rationale must be documented in detail in source records.

If the Investigator determines it is necessary to alter postdose spirometry, the decision applies only to the current visit. At all subsequent study visits, efforts to implement the proposed schedule of assessments should be renewed.

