**Appendix 5: Schedule of Assessments**

**Table 1: Schedule of Assessments – Part A (Single Dose)**

Study Epoch	Screening	Treatment			Follow-up	
Study Procedures	Screening	Day 1 predose	Day 1 dosing & postdose	Days 2 & 3	Safety Follow-up	Additional Follow-up
Study Day (Window)	-28 to -1	1	1	2 & 3	7 (+3)	14 (±3)
Informed consent	X					
Inclusion/exclusion criteria	X	X				
Demographic data a	X					
Medical history	X	X b				
Body weight and height	X				X c	
Oral body temperature	X	X d	X	X	X	X
Blood pressure and pulse rate	X	X d	X e	X	X	X
SpO 2	X	X d	X e	X	X	X
Physical examination	X	X	X f	X f	X f	X f
Pregnancy test g	X	X			X	
Follicle-stimulating hormone h	X					
12-lead ECG	X	X	X i	X	X	
HRCT	X j					
Spirometry k	X	X l	X l	X	X	X
Carbon monoxide diffusion capacity k	X	X d		X	X	X
Clinical chemistry and hematology	X	X		Day 3 only	X	
Serology	X					
Urine drugs of abuse screen m	X					
██████████ ██████████		██████████	██████████	██████████		
Nonresidential visit	X			Day 3 only	X	X
Study treatment administration			X			
Adverse event recording		X	X	X	X	X
██		██████████				
Pharmacokinetic blood sampling		X	X o			
██		██████████			██████████	██████████

Note, where multiple assessments are required at a single timepoint, the following order of procedures should be used: blood sampling, spirometry, other procedures (ECGs should be scheduled before vital signs measurements). See also footnote k.

Note, timing of safety and pharmacokinetic assessments may be changed based upon findings from previous cohorts.

Abbreviations: ECG = electrocardiogram; HRCT = high-resolution computed tomography; SpO2 = oxygen saturation.

- a To include smoking history.
- b Interim medical history.
- c Height measured only at Screening.
- d Within 60 minutes prior to dosing.
- e 1 hour and 2 hours after completion of dose administration.
- f Symptom-directed physical examination.

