- g In women of childbearing potential. Blood pregnancy test will be performed at Screening and Safety Follow-up; urine pregnancy test will be performed at Day 1. If the Day 1 pregnancy test is positive, dosing of that subject should not proceed. If there is doubt over the accuracy of a positive urine pregnancy test result, a blood pregnancy test must be obtained through the central laboratory to confirm the result. A local blood pregnancy test may also be performed if considered to be in the best interest of the subject (eg, travel planning). If the local test is negative and there are no other clinical findings suggestive of pregnancy, the subject may be dosed.
- h In postmenopausal women (at least 12 months postcessation of menses without an alternative medical cause) only, to confirm postmenopausal status. Confirmation of postmenopausal status requires level >40 mIU/mL in addition to appropriate history (refer to [Section 6.5](#)).
- i 2 hours after completion of dose administration.
- j If the most recent historical HRCT was performed more than 12 months prior to the initiation of Screening OR if the HRCT performed within 12 months prior to the initiation of Screening is determined not to be of suitable quality by the central over-reader, the imaging study must be repeated during Screening. Any HRCT used to establish subject eligibility must undergo central interpretation.
- k Spirometry should preferably be performed before carbon monoxide diffusion capacity assessments at timepoints where both assessments are required, but if not feasible, the rationale should be documented in source records and the order of testing implemented on Day 1 should be used at every subsequent study visit.
- l Completion of a minimum of 3, maximum of 6 forced expiratory maneuvers within 60 minutes predose. Preferably 3 but a minimum of 2 maneuvers as soon as feasible but within 15 minutes after completion of dose administration and at 30 ± 5 minutes, 60 ± 10 minutes, and 90 ± 15 minutes after completion of dose administration (up to a maximum of 16 forced expiratory maneuvers per day).
- m Exclusionary only if positive for a drug or metabolite of a drug that has not been prescribed and that remains positive on repeat testing.
- n [REDACTED]

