10.1.2 Repeat and Unscheduled Readings

Repeat readings occur when the original vital signs or ECG result requires confirmation. Repeat readings are labelled as 'Repeat' in the listings and replace the original readings in all summaries and changes from baseline presentations and calculations. Prior to dosing, all readings taken in addition to the original reading are defined as predose repeats. Postdose repeat readings are defined as readings collected within 15 minutes of the actual time of the original reading. Where results are taken in triplicate and repeated, the last 3 readings are used in all subsequent calculations.

With the exception of predose results described above, unscheduled readings for vital signs or ECGs are defined as readings collected >15 minutes from the actual time of the original reading. Where results are taken in triplicate, the original reading is defined as the first reading of the triplicate. All results not taken at a scheduled timepoint for other data types (eg, clinical laboratory parameters) are unscheduled. Unscheduled readings are labelled as 'Unscheduled' in the listings. Because unscheduled readings are not associated with any scheduled timepoint, they are excluded from all summaries (with the exception that they may be used as baseline, as stated in Section 10.1.1).

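### Out-of-range vital signs give way to their repeats and unscheduled readings enter no summary; only QTc has an explicit all-readings table, so a transient extreme can be absent from the by-treatment tables

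*SAP*

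**What the plan says.** **Vital signs.** Protocol 7.1.3 takes the Day 1 predose blood pressure, pulse rate and respiratory rate in triplicate. After that, "All subsequent measurements will be performed singly and repeated once if outside the relevant clinical reference ranges". No time limit is set for the repeat.

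**Repeats.** SAP 10.1.2 applies to vital signs and ECGs: "Postdose repeat readings are defined as readings collected within 15 minutes of the actual time of the original reading". Such repeats "replace the original readings in all summaries and changes from baseline presentations and calculations". SAP 10.1 lists the minimum and maximum among the summary statistics, so they are covered too.

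**Unscheduled readings.** A vital-sign or ECG reading more than 15 minutes from the original is unscheduled. So is any result of another data type that was not taken at a scheduled timepoint. The consequence is: "Because unscheduled readings are not associated with any scheduled timepoint, they are excluded from all summaries". The one exception named there is use as baseline.

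**Outputs.** SAP 10.6.4 plans a QTcB and QTcF outlier analysis on every individual postdose measurement, repeat and unscheduled readings included. SAP 10.6.3 (vital signs), 10.6.5 (SpO2) and 10.6.6 (FEV1, FVC) plan summaries, changes from baseline and listings, with no all-readings table.

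**Timing.** In both schedules (Protocol Appendix 5), postdose blood pressure, pulse and SpO2 on dosing days are due at "1 hour and 2 hours after completion of dose administration". Postdose spirometry is due within 15 minutes and then at "30 ± 5 minutes, 60 ± 10 minutes, and 90 ± 15 minutes after completion of dose administration".

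**The concern.** The trigger for a repeat is the abnormality itself. In-range values are never overwritten; out-of-range values are, whenever the re-measurement comes within 15 minutes. A short-lived rise or fall in blood pressure after inhalation could therefore be recorded, confirmed as having passed, and then be missing from every by-treatment statistic.

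The unscheduled rule has a similar effect by another route. Protocol 7.1.3 foresees extra measurements: "Vital signs may also be performed at other times if judged to be clinically appropriate". Readings taken because someone suspected a problem are the ones most likely to fall off the schedule.

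Protocol 2.2.1 makes vital signs, SpO2, FEV1 and FVC primary safety endpoints. No inferential safety analysis is planned, so the descriptive tables are the main by-treatment evidence. With so few active subjects per dose, one missing event can change what a table shows.

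**Working it through.** The documents give no sample-size, power or error-rate figure that bears on this point. The check is a trace of the rules, followed by arithmetic and an illustration.

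**1. Group sizes** (Protocol 3.1.1 and 3.1.2). Part A: 4 cohorts × (3 active + 1 placebo) = 16. Part B: 3 cohorts × (4 active + 2 placebo) = 18. Both match the plan. Pooled placebo is 4 in Part A and 6 in Part B.

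**2. Fate of an abnormal postdose reading**

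| Reading | Rule in SAP 10.1.2 | In by-treatment summaries? |
|---|---|---|
| Vital sign out of range, repeat at 14 min | Repeat replaces it | No |
| Same vital sign, re-measured at 16 min | Second reading is unscheduled | Original yes, second no |
| Extra vital sign off schedule | Unscheduled | No |
| SpO2, FEV1 or FVC at a scheduled time | Repeat rule does not reach these data | Yes |
| SpO2, FEV1 or FVC off schedule | Unscheduled, if so classed | No |
| QTcB or QTcF, any reading | Brought back by SAP 10.6.4 | Yes, in the outlier table |

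The first two rows show that the same abnormal value stays or goes according to when it is re-measured, and the protocol does not fix that time.

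**3. Overlap of schedules.** Scheduled blood pressure and SpO2 fall at 60 and 120 minutes. The spirometry windows are 0–15, 25–35, 50–70 and 75–105 minutes. Only 50–70 contains a scheduled blood pressure and SpO2 time. So 3 of the 4 postdose spirometry times have no concurrent scheduled reading, and one taken then would be off schedule.

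**4. Exact arithmetic for one replaced value.** Shift in group mean = (original − repeat) / n. With 165 replaced by 135 mmHg: 30/3 = 10 mmHg, or 30/4 = 7.5 mmHg. A count of affected subjects goes from 1/3 (33%) or 1/4 (25%) to 0.

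**5. Illustration of a transient.** Every input is assumed: systolic range 90–140 mmHg, mean 115, 125 or 130, between-subject SD 12, reading SD 6, 8 or 10. One active subject is raised by 30 mmHg at the original reading, and a stated share of that rise remains at the repeat. Out-of-range readings are replaced by the repeat. There are 400,000 simulated groups per cell. Results are averaged over groups in which that subject's original exceeds 140, and ranges are over the grid.

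| Active n | Rise left at repeat | Repeat in range | Fall in group maximum (mmHg) | Fall in group mean (mmHg) |
|---|---|---|---|---|
| 3 | 0–50% | 31–95% | 13.1–25.7 | 5.5–11.7 |
| 4 | 0–50% | 31–95% | 12.3–23.8 | 4.1–9.3 |
| 3 | 75% | 13–42% | 7.1–10.4 | 3.0–4.2 |
| 3 | 100% | 3–23% | 0.3–3.6 | 0.5–1.7 |

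The loss is large for an effect that fades quickly and small for one that lasts.

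**6. Noise in an all-readings count.** Same assumed range, means and SDs, no treatment effect, 8 scheduled Part B postdose readings per subject (2 × 4 visits). Between 19% and 65% of subjects have at least one out-of-range systolic reading. Of those, 56–91% have a true value inside the range.

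**The case against.** **The repeat rule is a sound convention.** It was set in advance and removes measurement noise. Step 6 of the working supports that: most unaffected subjects flagged on any single reading would be false alarms. This stands. It is a reason to keep the rule in the by-timepoint summaries and to separate confirmed from unconfirmed values in any new table.

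**Nothing is deleted.** Repeats and unscheduled readings appear, labelled, in the listings, which are short at 3 or 4 active subjects per dose. Extremes reported as adverse events reach the treatment-emergent tables (SAP 10.6.1). This also stands. It narrows the point to the summaries of the endpoints themselves.

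**Early lung-function changes are covered.** Protocol 7.1.8 says "Greater emphasis should be placed on proper assessment closer to the time when treatment is completed than at later times". A reader might infer that the SAP discards what the protocol most wants to see. The documents do not support that: the sentence concerns spirometry, and the early spirometry sessions are scheduled and summarized with their minimum and maximum. Only sessions that the Investigator times outside the schedule are exposed, and SAP 10.1.2 does not clearly say how they are classed.

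**The SpO2 route is conditional.** Protocol 7.1.7 lacks the express allowance for extra measurements that 7.1.3 gives for vital signs. Both schedules also let timings change after earlier cohorts, so added early readings could become scheduled. The rule's effect on an off-schedule SpO2 reading is clear; how often one would be taken is not.

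**QTc is not quite alone.** SAP 10.6.2 summarizes out-of-range laboratory data by treatment. That qualifies any broad statement about QTc, but it does not help vital signs, SpO2 or spirometry.

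**Other documents may fill the gap.** The table and listing shells that SAP section 4 mentions are not among the documents, so the point is about the SAP text.

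**Conclusion.** The point holds in a limited form. As written, the SAP removes an out-of-range postdose vital sign from all by-treatment summaries if it is repeated within 15 minutes, and it keeps unscheduled vital-sign, SpO2 and spirometry readings out of every summary. It makes an explicit all-readings exception for QTc and none for these primary safety endpoints.

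This rests on the text and the group sizes alone. The mmHg ranges depend wholly on assumed inputs and on an assumed event. They show how the rule acts and do not estimate an expected loss.

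Two stronger conclusions might be inferred. One is that dose escalation would proceed on incomplete data; Protocol 8.6 gives the data monitoring committee all available safety data, so the documents do not support it. The other is that the safety analysis is invalid; the plan is descriptive, its rules are stated in advance and the values are listed. This is a gap in the reported tables that should be closed because it is cheap to close.

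**What to change.** Keep the by-timepoint summaries and the repeat rule. In the SAP:

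1. Add to 10.6.3 and 10.6.5 by-treatment tables, with pooled placebo, of each subject's worst postdose value and largest change from baseline for vital signs and SpO2. Show SpO2 with the oxygen supply at the time, since Protocol 7.1.7 provides for readings on and off oxygen.
2. Add to 10.6.6 a table of the largest decline from predose in FEV1 and FVC.
3. Use all original, repeat and unscheduled readings in these tables, as 10.6.4 does for QTc.
4. If out-of-range vital signs are counted, count those confirmed and those not confirmed on repeat separately.
5. Name these tables and the 10.6.4 analysis as exceptions in 10.1.2.

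The cost is SAP wording and about three tables from data already collected, with no new assessment and no protocol change. The drawback is that unconfirmed noise will appear fairly often. The tables must be read against pooled placebo, which is only 4 or 6 subjects in the planned cohorts, and against the labelled repeats in the listings.

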10.2 Demographics and Subject Disposition

The demographic variables age, sex, race, ethnicity, body weight, height, and body mass index will be summarized and listed. Subject disposition will be summarized and listed.

10.3 Pharmacokinetic Assessment

10.3.1 Pharmacokinetic Analysis

The following pharmacokinetic parameters will be determined where possible from the whole blood concentrations of TRK-250 using non-compartmental methods performed using Phoenix WinNonlin (Version 8.1 or higher):

Parameter	Definition
$AUC_{(0-t_{last})}$	area under the concentration-time curve (AUC) from time zero to the last quantifiable concentration,
C_{max}	maximum observed concentration
T_{max}	time of maximum observed concentration

Additional pharmacokinetic parameters may be determined where appropriate.

Pharmacokinetic analysis will, where possible, be carried out using actual postdose times recorded in the raw data. If actual times are missing, nominal times may be used with sponsor approval.

Concentrations are used as supplied by the analytical laboratory for PK analysis. The units of concentration and resulting PK parameters, with amount or concentration in the unit, will be presented as they are received from the analytical laboratory.

C_{max} and T_{max} will be obtained directly from the plasma concentration-time profiles.

For multiple peaks, the highest postdose concentration will be reported as C_{max} . In the case that multiple peaks are of equal magnitude, the earliest T_{max} will be reported.

10.3.2 Criteria for Handling Concentrations Below the Limit of Quantification in

Pharmacokinetic Analysis

- Concentration values that are below the limit of quantification (BLQ) will be set to zero, with defined exceptions as follows:
 - Any embedded BLQ value (between 2 quantifiable concentrations) and BLQ values following the last quantifiable concentration in a profile will be set to missing for the purposes of PK analysis.
 - If there are late positive concentration values following 2 BLQ concentration values in the apparent terminal phase, these values will be evaluated. If these values are considered to be anomalous, they will be set to missing.
 - If an entire concentration-time profile is BLQ, the profile will be excluded from the PK analysis.
 - If a predose concentration is missing, these values will be set to zero.

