9 DEFINITION OF ANALYSIS POPULATIONS

The **Safety Population** will include all subjects who received at least 1 dose of study treatment (TRK-250 or placebo) and have at least 1 postdose safety assessment.

The **Pharmacokinetic (PK) Population** will include all subjects who received at least 1 dose of TRK-250 and have evaluable PK data.

The **All Subjects Population** will consist of any subjects who signed informed consent and had study assessments recorded on the database as per the protocol.

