10 STATISTICAL METHODOLOGY

10.1 General

Data listings will be provided for the All Subjects Population. Summary statistics and statistical analyses will be performed for subjects included in the relevant analysis populations

For continuous data, summary statistics will include the arithmetic mean, arithmetic standard deviation, median, minimum, maximum, and number. For log-normal data (eg, the PK parameters: areas under the concentration-time curve [AUCs] and maximum observed concentration [C_{max}]), the geometric mean and geometric coefficient of variation (CV%) will also be presented. For categorical data, frequency counts and percentages will be presented. Data listings will be provided for all subjects up to the point of withdrawal, with any subjects excluded from the relevant population highlighted. For the calculation of summary statistics and statistical analysis, unrounded data will be used.

Missing values will not be imputed.

Data analysis will be performed using SAS[®] Version 9.4 or greater.

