10.3.3 Calculation of AUC

- AUC values will be calculated using the linear trapezoidal rule for increasing concentrations and the logarithmic trapezoidal rule for decreasing concentrations.
- The minimum requirement for the calculation of AUC will be the inclusion of at least 3 consecutive whole blood concentrations above the lower limit of quantification (LLOQ), with at least 1 of these concentrations following C_{max} .
- For any partial AUC determination (if required), nominal time will generally be used for the end of the interval. Actual times for partial AUC intervals may be used at the discretion of the Pharmacokineticist.

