10.4 Presentation of Pharmacokinetic Data

10.4.1 Presentation of Pharmacokinetic Concentration Data

The following rules will be applied if there are values that are BLQ or if there are missing values (e.g., no result [NR]) in a plasma or whole blood concentration data series to be summarized.

- For the calculation of summary statistics, BLQ values will be set to zero.
- If an embedded BLQ value is considered anomalous within the concentration-time profile, this value will be excluded from the summary statistics.
- Where there is NR, these will be set to missing.
- If there are less than three values in the data series, only the min, max and N will be presented. The other summary statistics will be denoted as not calculated (NC). BLQ is considered a value.
- If all the values are BLQ, then the arithmetic mean, arithmetic SD, median, min and max will be presented as zero, and the geometric mean and geometric CV% will be denoted as NC.
- If the value of the arithmetic mean or median is below the lower limit of quantification, it will be presented as zero and the geometric mean and geometric CV% will be denoted as NC.

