10.4.2 Presentation of Pharmacokinetic Parameters

- For the calculation of summary statistics of PK parameters, all NR and NC values in a data series will be set to missing.
- The AUC values will be set to NC if they have been calculated using fewer than three concentrations, and/or three concentrations if the last is C_{\max} .

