10.4 Pharmacokinetic Statistical Methodology

Where data available blood concentration of TRK-250 and corresponding PK parameters will be summarized and listed. PK concentration profiles over time will be presented graphically.

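### Dropping wholly BLQ profiles biases mean Cmax upward in cohorts that also have quantifiable profiles, and the 5% predose exclusion should be limited to first-dose profiles

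*SAP*

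**What the plan says.** **Wholly BLQ profiles.** The default in SAP 10.3.2 sets BLQ concentrations to zero. One exception reads: "If an entire concentration-time profile is BLQ, the profile will be excluded from the PK analysis". No Cmax is then derived. In the parameter summaries of SAP 10.4.2, "all NR and NC values in a data series will be set to missing", and SAP 10.1 rules out imputation. The PK Population in SAP 9 "will include all subjects who received at least 1 dose of TRK-250 and have evaluable PK data"; the term *evaluable* is not defined.

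**What stays visible.** For the concentration tables, SAP 10.4.1 says: "For the calculation of summary statistics, BLQ values will be set to zero". SAP 10.4 (Pharmacokinetic Statistical Methodology) adds that "blood concentration of TRK-250 and corresponding PK parameters will be summarized and listed". SAP 10.1 lists the statistics for continuous data as "the arithmetic mean, arithmetic standard deviation, median, minimum, maximum, and number", with geometric mean and geometric CV% added for Cmax and AUC.

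**Predose rules.** SAP 10.3.2: "If a predose concentration is missing, these values will be set to zero". SAP 10.3.4 lets the pharmacokineticist leave a subject's parameters out of the summaries when a quantifiable predose value exceeds 5% of Cmax. Neither rule names a day or study part.

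**Design.** Each planned cohort has 3 active subjects in Part A and 4 in Part B (Protocol 3.1.1, 3.1.2). Blood is sampled predose, within 5 minutes, and at 10, 30 and 60 minutes after dosing: on Day 1 in Part A, and on Days 1 and 22 in Part B (Protocol Appendix 5). Day 22 follows three weekly doses.

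**The concern.** A wholly BLQ profile is not missing information. It shows that Cmax was below LLOQ. Removing it leaves a summary conditional on detection, so exposure looks higher than it was in the dosed cohort. If exposure rises with dose, the loss falls mainly on low-dose cohorts and flattens the apparent dose–exposure relation.

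The 5% rule makes sense on Day 1: prior TRK-250 is an exclusion criterion, so a quantifiable predose value should not occur. On Day 22 a quantifiable predose value may be genuine carry-over. The rule could then remove exactly the subjects who show it from the multiple-dose summary.

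Blood PK after single and multiple doses is the secondary objective, and Protocol 1.7 expects it to inform off-target potential. No test, sample size or direct safety decision depends on these summaries.

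**Working it through.** The documents give no figure to reproduce. LLOQ, expected Cmax, its variability and the blood half-life are all absent, so each is an assumption shown as a range.

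**1. Direction of the bias, with no distribution assumed.** Take n active subjects of whom m are wholly BLQ (0 < m < n). Every retained Cmax is at or above LLOQ and every dropped one is below it, so the retained mean and geometric mean must exceed those of all n. For the arithmetic mean the largest possible ratio, with dropped values at zero, is n/(n−m):
- n = 3: 3/2 = 1.5 (m = 1); 3/1 = 3.0 (m = 2)
- n = 4: 4/3 = 1.33 (m = 1); 4/2 = 2.0 (m = 2); 4/1 = 4.0 (m = 3)

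With m = 0 there is no bias. With m = n there is no Cmax summary.

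**2. Size for an assumed log-normal Cmax.** Set LLOQ = 1, GM = true geometric mean, σ = √ln(1+CV²), a = −ln(GM)/σ, p = 1−Φ(a). The expected inflation of the geometric mean (log scale) is exp(σφ(a)/p), and P(mixed cohort) = 1 − pⁿ − (1−p)ⁿ. Example: CV 60% gives σ = 0.555. At GM = 2, a = −1.25, p = 0.894 and inflation is 1.12.

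| True GM | Inflation, CV 30/60/100% | P(mixed), n = 3 | P(mixed), n = 4 |
|---|---|---|---|
| 1 × LLOQ | 1.26 / 1.56 / 1.94 | 75% at any CV | 88% at any CV |
| 2 × LLOQ | 1.01 / 1.12 / 1.34 | 3 / 28 / 49% | 4 / 36 / 59% |
| 5 × LLOQ | 1.00 / 1.00 / 1.05 | 0 / 1 / 8% | 0 / 1 / 10% |

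**3. How many cohorts.** Assume dose-proportional exposure and CV 60%. If GM equals LLOQ at 2 mg, the chance of a mixed cohort at 2, 10, 30 and 60 mg is 75, 0.6, 0 and 0%. If GM equals LLOQ at 10 mg, it is 0.6, 75, 7 and 0.2%. The problem sits in cohorts near LLOQ.

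**4. AUC.** SAP 10.3.3 needs three consecutive quantifiable values with one after Cmax, and there are four postdose samples. The number of subjects with an AUC can therefore be smaller than the number with a Cmax.

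**5. When the 5% rule is reached on Day 22.** Assume one compartment, a 168 h interval and three earlier doses. With half-life t, r = 2^(−168/t), S = r + r² + r³ and predose/Cmax = S/(1+S).
- t = 12, 24, 36 h: 0.01, 0.8, 3.9% (not reached)
- t = 48, 84, 168 h: 8.8, 24.7, 46.7% (reached)
- The ratio equals 5% at t = 38.9 h. Example at 48 h: r = 0.0884, S = 0.0969, ratio 0.0969/1.0969 = 8.8%.

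**6. Missing Day 22 predose set to zero.** Same model, half-life 48–168 h, linear-up/log-down AUC over the protocol times, nebulization assumed to last 0 to 20 minutes. AUC falls by 0.2–0.9% if true predose is 5% of Cmax and by 1.1–4.4% if it is 25%. Cmax does not change. Leaving out the first segment instead would lose roughly 5–22%.

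**The case against.** Several safeguards stand. With 3 or 4 active subjects, a Cmax n of 2 is easy to notice. The listings mark excluded subjects, and the concentration tables keep BLQ as zero. The table shells are not available and may already carry a BLQ count. What remains is that n alone does not say why a subject is absent, and no rule in the SAP asks for a count of quantifiable profiles.

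A geometric mean cannot include a <LLOQ value without substitution, which SAP 10.1 does not allow. That also stands. A remedy that only labels the geometric mean leaves the bias in place, so another statistic has to lead.

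The 5% exclusion is permissive, and SAP 10.3.4 asks for strong justification and documentation when data are excluded. But that requirement is attached to anomalous points. The 5% provision mentions only discretion.

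Four stronger readings are tempting and are not supported:
- *The parameter and concentration tables contradict each other.* They do not, if a wholly BLQ subject counts as evaluable. The undefined term leaves this open.
- *The inflation affects the whole dose range.* Step 3 shows that it concentrates near LLOQ, and LLOQ is not given.
- *Setting a missing predose to zero distorts Day 22.* The effect is negligible, and a zero start loses less than omitting the segment.
- *No other sample could separate carry-over from an anomaly.* The Day 1 decline helps: from 5 to 60 minutes concentration falls 47% at a 1 h half-life but 1.6% at 39 h. Day 22 predose values of other subjects in the cohort help too.

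**Conclusion.** The point holds in two parts.

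(a) In any cohort with both wholly BLQ and quantifiable profiles, the stated rules make the mean and geometric mean Cmax too high. The direction is certain. The size depends on an assumed log-normal Cmax and an unknown LLOQ: substantial when true Cmax is near LLOQ, and small to nil once it is several times LLOQ. The maximum is unaffected. Sample counts, listings and concentration tables reveal part of the loss.

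(b) The 5% predose exclusion has no day limit and could remove real carry-over from the Day 22 summaries. In the assumed one-compartment model this arises only with a blood half-life of about 39 h or more, and the documents neither support nor exclude that.

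PK is descriptive and subject safety is not directly affected. This is a minor correction, worth making because it costs little.

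**What to change.** **SAP 9, 10.3.2 and 10.4.2**
- State that a wholly BLQ profile is evaluable.
- Count its Cmax as <LLOQ in n, median and minimum. Tmax is missing and AUC is not calculated.
- Report *n quantifiable / n dosed* per cohort and day beside the Cmax and AUC summaries.
- In cohorts with any wholly BLQ profile, make median and range the main Cmax summary. Show arithmetic mean, SD, geometric mean and geometric CV% only if labelled *quantifiable profiles only*.
- State how the median is shown when it falls between a <LLOQ value and a quantified one (possible with n = 4 and two BLQ profiles), for example as an upper bound.

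**SAP 10.3.4**
- Limit the 5% predose rule to first-dose (Day 1) profiles. Keep Day 22 subjects with quantifiable predose in the summaries.

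**SAP 10.3.2, missing predose**
- No change is needed. At most, flag a Day 22 AUC calculated with a missing predose value.

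**Cost.** SAP wording and one row in the PK tables; wording only, if the shells already have that row. The downside is that low-dose cohorts may show lower or <LLOQ exposure.
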